4.4 Secondary Safety Outcomes

Both Arms:

- 1. Incidence of SICH, by ECASS III definition, within 24 (-6/+24) hours post randomization (time zero)
- Incidence of neurological deterioration from baseline NIHSS score through Day 5-7/discharge (whichever is earlier) post randomization (time zero). Neurological deterioration is defined as ≥ 4 point increase in the NIHSS score from the baseline score.

Document Number: CDM10000146

Treatment Arm only:

- 3. Incidence of procedure-related and device-related serious adverse events (PRSAEs and DRSAEs) through 24 (-6/+24) hours post randomization (time zero), as adjudicated by the clinical events committee (CEC), and defined as:
 - vascular perforation
 - intramural arterial dissection
 - embolization to new territory
 - access site complication requiring surgical repair or blood transfusion
 - intra-procedural mortality
 - device failure (*in vivo* breakage)
 - any other complications adjudicated by the CEC to be related to the procedure

5 Study Design

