7.5 End of the Trevo Thrombectomy Procedure (Treatment arm only)

The Trevo thrombectomy procedure should be terminated if any of the following occur:

- 1. Neurological deterioration or alteration in function is detected leading to the suspicion of an intracranial hemorrhage
- 2. The time from groin puncture reaches 2 hour
- 3. TICI grade 2b or 3 flow (reperfusion of > 2/3 MCA territory) is established
- 4. The occlusion is refractory to six retrieval attempts in a single vessel

Neurological deterioration or alteration in function leading to the suspicion of an intracranial hemorrhage will necessitate an emergent head CT or MRI scan. At the discretion of the investigator, this evaluation may also include angiography or other diagnostic tests to

Document Number: CDM10000146

determine the etiology of the clinical alteration. Management of an intracranial hemorrhage will be performed according to each institution's usual practice.

7.6 24 (-6 / +24) Hours post Randomization

The following data will be collected at 24(-6/+24) hours post randomization:

- In hospital medical management details
- NIHSS
- MRI/MRA or CT/CTA in order to assess for hemorrhage, vessel patency and infarct core volume. The same imaging modality should be used at 24 (-6/+24) hours to measure vessel patency as was used at baseline to identify occlusion location. MRI T2 Flair or CT may be used to assess core infarct volume.
- Adverse events and any treatment administered

For all subjects who expire prior to the 24 (-6/+24) hour assessment, available information regarding the primary cause of death and date/time of death will be recorded, as well as whether the subject was made "do not resuscitate" (DNR) or "comfort care only" prior to expiration.

Deaths MUST be reported to Stryker NV within 24 hours of becoming aware, preferably by CRF completion. In the event that the EDC system is unavailable a written report by e-mail or fax is acceptable.

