8.7.3 Other Pre-planned Analyses

Both Arms:

1. Incidence of symptomatic ICH (per the SITS MOST definition)

Treatment Arm only:

2. Frequency of functional independence (mRS 0-2) by reperfusion status postdevice and post-procedure

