Subdural hemorrhage: Blood between the dura mater and the skull.

Symptomatic ICH (SICH): The primary protocol definition is adapted from ECASS III as any apparently extravascular blood in the brain or within the cranium that is associated with clinical deterioration as defined by an increase of four points or more in the NIHSS, or that led to death and was judged to be the predominant cause of a neurologic deterioration. The SITS-MOST definition of SICH is: Any PH-2 with a four point or more increase in NIHSS.

Unanticipated Serious Adverse Device Effects (USADEs): A subset of SADEs that are unanticipated, or not previously identified in the labeling of the investigational device, including the Investigator Brochure, Clinical Investigational Plan and Informed Consent Form

Vessel Perforation: A hole or puncture (perforation) in the vessel wall that occurs unintentionally during the index procedure. The perforations may be seen angiographically during the index procedure by frank or free extravasation of the contrast into the surrounding tissue or blush or localized contrast extending outside the vessel lumen.

Weighted mRS: A numerical value representing the clinical utility of each mRS category.

Document Number: CDM10000146

Rev: AD

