4.15.7. Other Pre-planned Analyses

Both Arms:

Incidence of symptomatic ICH (per the SITS MOST definition) will be presented by providing the count and percentage for each treatment arm. The difference in the percentage between two arms and the 95% CI for the difference will be calculated using the normal approximation to binomial. P-values will be calculated by the Chi-squared test or Fisher's exact test as appropriate. Relative Risk (RR) was provided as Trevo thrombectomy plus medical management / medical management.

Treatment Arm only:

Summary of functional independence (mRS 0-2) by reperfusion status, will be provided by N, percentage and exact Clopper-Pearson 95% CI, separately by post-device and post-procedure in treatment arm.

Document Title: DAWN™ Trial Statistical Analysis Plan

Document Number: CDM10000704

Rev: AB

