6.3. Rules for Calculating Rates and Handling Denominators

For Safety events, binary rates will be calculated using as a denominator as the number of all Subjects in the study, regardless of their follow-up time.

Stryker Neurovascular

Document Title: DAWN™ Trial Statistical Analysis Plan

Document Number: CDM10000704

Rev: AB

Other binary rates such as mRS or NIHSS will be calculated using a denominator as the total number of the available data for the outcome, excluding missing values.

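### The SITS-MOST definition of symptomatic ICH has no death criterion, so a PH-2 that is fatal before any further NIHSS can be left out of that count

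*Protocol*

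**What the plan says.** Appendix B defines SICH twice in one entry. The first definition, adapted from ECASS III and named as the primary one, is met by extravascular blood with an NIHSS rise of at least four points, "or that led to death and was judged to be the predominant cause of a neurologic deterioration". The second reads: "The SITS-MOST definition of SICH is: Any PH-2 with a four point or more increase in NIHSS".

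The two definitions feed different analyses.

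- **ECASS III** is a secondary safety outcome with a time window (Protocol Section 4.4): "Incidence of SICH, by ECASS III definition, within 24 (-6/+24) hours post randomization (time zero").
- **SITS-MOST** is listed among the other pre-planned analyses for both arms (Protocol Section 8.7.3), with no window. SAP Section 4.15.7 adds the method: "Incidence of symptomatic ICH (per the SITS MOST definition) will be presented by providing the count and percentage for each treatment arm". A difference with 95% CI, a p-value and a relative risk follow. The SAP does not restate or extend the definition.

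On safety outcomes, SAP Section 6.3 says: "binary rates will be calculated using as a denominator as the number of all Subjects in the study, regardless of their follow-up time". Its next rule, for other binary rates such as mRS or NIHSS, removes missing values from the denominator.

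**The concern.** Both definitions use the NIHSS to show that a bleed was symptomatic, but only one says what happens when the patient dies. A programmer or adjudicator who reads them together could take the omission from the second as deliberate. The subjects affected would be those with the largest hemorrhages and the fastest fatal course, and these are the cases a symptomatic-hemorrhage rate should capture first. The analysis is a between-arm comparison with a p-value and relative risk, so a handful of unclassified fatal bleeds could shift a result that readers will set beside the ECASS III rate.

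**Working it through.** The documents state no expected SITS-MOST rate, sample size or power for this analysis, so there is no planned figure to reproduce. The check is whether any other rule fills the gap, and then how much one case is worth.

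**Step 1. Could a PH-2 be seen with no NIHSS after it?** Protocol Table 5 schedules NIHSS at baseline, 24 (-6/+24) hours, Day 5-7 or discharge, Day 30 and Day 90. The first post-baseline window opens at 24 − 6 = 18 hours. Protocol Section 7.5 provides for earlier imaging in the treatment arm: neurological deterioration "leading to the suspicion of an intracranial hemorrhage will necessitate an emergent head CT or MRI scan". That section does not ask for an NIHSS with the scan. The table footnote tying an NIHSS to imaging covers only the scheduled 24-hour scan. The situation is therefore possible.

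**Step 2. Does any rule supply an NIHSS at death?**

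- Protocol Section 7.6, for deaths before the 24-hour assessment: "available information regarding the primary cause of death and date/time of death will be recorded", with do-not-resuscitate or comfort-care status. No NIHSS is mentioned. Sections 7.8 and 7.9 treat later deaths the same way.
- SAP Section 4.8 scores a subject with no mRS after baseline as mRS 6. This concerns mRS only.
- SAP Section 6.2 has a general imputation condition (missingness linked to prognostic factors and above 20%). It assigns nothing to a death.

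No rule fills the gap.

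**Step 3. How is the subject then scored?** Let n be the arm size and k the other counted events. Correct classification gives (k + 1)/n.

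- Under the SAP 6.3 safety-event rule the subject is a non-event: k/n. Loss = 1/n.
- Under the SAP 6.3 rule that removes missing values the subject is excluded: k/(n − 1). Loss = (k + 1)/n − k/(n − 1) = (n − 1 − k)/[n(n − 1)]. This equals 1/n when k = 0 and falls slowly as k grows.

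Under neither rule is the subject counted as SITS-MOST SICH.

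**Step 4. Size of one case.** The maximum is 250 per arm (Protocol synopsis). The minimum trial size is 150, which is 150/2 = 75 per arm at 1:1.

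| Arm size | Loss per case (1/n) |
|---|---|
| 250 | 1/250 = 0.4 points |
| 75 | 1/75 = 1.3 points |

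**Step 5. Does ECASS III cover the same event?** Only in part. Its outcome stops at the 24 (-6/+24) hour window, while the SITS-MOST analysis states none. A PH-2 after that window, fatal before the Day 5-7 NIHSS, could miss both SICH counts and appear only in mortality.

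**The case against.** The strongest reply is that little is lost in practice, and most of it stands.

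- The definition asks for an NIHSS increase. It does not say that the increase must be recorded at a scheduled visit. The CEC adjudicates symptomatic ICH, neurological worsening and all deaths from source documents (Protocol Section 13.2.1). Its charter is not among the documents and may hold a rule for this case.
- The emergent scan in Section 7.5 follows a detected neurological change, so an unscheduled NIHSS may often exist. A fatal PH-2 with a documented four-point rise before death counts normally.
- Such a subject is not reported as hemorrhage-free. The CT/MR core lab still grades the bleed (Section 13.3.2), ECASS III SICH has a death criterion, and the death enters all-cause mortality and is assessed for stroke-related mortality, the primary safety outcome.
- The two SICH rates may differ by design, since one takes any extravascular blood and the other only PH-2. A difference between them is not in itself an error.

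A reader might also infer that the omission makes Trevo look safer by a sizeable margin. The documents do not support this. Table 4 of the protocol shows symptomatic ICH of 10% in the Pre-DAWN cohort and 2% in the PROACT II controls. However, Section 5.2.1 gives the definition in the parent cohort of the first group as PH-1 or PH-2, and Section 1.3 describes those controls as treated with intra-arterial heparin within 0-6 hours. Section 5.2.4 reports 7% in reperfused against 19% in non-reperfused target-mismatch patients, which points the other way, although that is not a treated-versus-untreated comparison either. No passage gives the share of PH-2 cases that die before another NIHSS.

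The omission in the definition itself survives these points. The protocol and SAP do not state the rule, and a published analysis definition should not depend on an unstated one.

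**Conclusion.** The point holds as a minor correction. As written, the SITS-MOST definition cannot be met through death alone, and nothing in the protocol or SAP supplies the missing NIHSS. A fatal PH-2 without a post-hemorrhage NIHSS can therefore be left out of that numerator. Each such case is worth 0.4 points of an arm's rate at 250 per arm and about 1.3 points at 75. The number of cases, their split between arms and hence the direction of any bias are unknown.

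This rests on three conditions: imaging shows the PH-2, no NIHSS follows the bleed, and the CEC charter contains no overriding rule. No primary or secondary outcome and no stopping rule uses the SITS-MOST rate. Whether the protocol's sentence matches the external definition it names cannot be checked from these documents. The conclusion depends only on the wording and its contrast with the ECASS III definition.

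**What to change.** In Appendix B, define SITS-MOST SICH as any PH-2 with an NIHSS increase of four points or more, or that led to death as adjudicated by the CEC. Restate that definition in SAP Section 4.15.7 so that the analysis does not depend on a cross-reference.

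The cost is one clause in two places. No new data are needed, because the core lab grades the hemorrhage and the CEC already adjudicates symptomatic ICH and every death. The downside is that the SITS-MOST rate may come out slightly higher.

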Appendix C. Angiographic Core Lab Scales

TIMI Grade Scale

- **0** No perfusion
- 1 Penetration with minimal perfusion

2a - Partial perfusion of the artery & its main branches < 50%

2b - Partial perfusion of the artery & its main branches \geq 50%

3 - Complete perfusion

Collateral Flow Grade

0 - No collaterals visible to the ischemic site

1 - Slow collaterals to the periphery of the ischemic site with persistence of some of the defect

2 - Rapid collaterals to the periphery of ischemic site with persistence of some of the defect and to only a portion of the ischemic territory

3 - Collaterals with slow but complete angiographic blood flow of the ischemic bed by the late venous phase

4 - Complete and rapid collateral blood flow to the vascular bed in the entire ischemic territory by retrograde perfusion

AOL Grade

0 - No recanalization of the primary occlusive lesion

I - Incomplete or partial recanalization of the primary occlusive lesion with no distal flow

II - Incomplete or partial recanalization of the primary occlusive lesion with any distal flow

III - Complete recanalization of the primary occlusion with any distal flow

TICI Scale

0 - No Perfusion - No antegrade flow beyond the point of occlusion

1 - Penetration with Minimal Perfusion - The contrast material passes beyond the area of obstruction but fails to opacify the entire cerebral bed distal to the obstruction for the duration of the angiographic run

2 - Partial Perfusion - The contrast material passes beyond the obstruction and opacifies the arterial bed distal to the obstruction; However, the rate of entry of the contrast into the vessel distal to the obstruction and/or its rate of clearance from the distal bed are perceptibly slower than its entry into and/or clearance from comparable areas not perfused by the previously occluded vessel, e.g. the opposite cerebral artery of the arterial bed proximal to the obstruction

- **2a** Only partial filling (<2/3) of the entire vascular territory is visualized
- **2b** Complete filling ($\geq 2/3$) of all the expected vascular territory is visualized, but the filling is slower than normal

3 - Complete Perfusion - Antegrade flow into the bed distal to the obstruction occurs as promptly as into the obstruction and clearance of contrast material from the involved bed is as rapid as from an uninvolved other bed of the same vessel or the opposite cerebral artery

Document Number: CDM10000146

Modified TICI Scale (mTICI Scale)

0 - No Perfusion - No antegrade flow beyond the point of occlusion

1 - Penetration with Minimal Perfusion - The contrast material passes beyond the area of obstruction but fails to opacify the entire cerebral bed distal to the obstruction for the duration of the angiographic run

2 - Partial Perfusion - The contrast material passes beyond the obstruction and opacifies the arterial bed distal to the obstruction; However, the rate of entry of contrast into the vessel distal to the obstruction and/or its rate of clearance from the distal bed are perceptibly slower than its entry into and/or clearance from comparable areas not perfused by the previously occluded vessel, e.g., the opposite cerebral artery or the arterial bed proximal to the obstruction

2a - Only partial filling (< 50%) of the entire vascular territory is visualized

2b - Filling of \geq 50% all of the expected vascular territory is visualized, but the filling is slower than normal

3 - Complete Perfusion - Antegrade flow into the bed distal to the obstruction occurs as promptly as into the obstruction and clearance of contrast material from the involved bed is as rapid as from an uninvolved other bed of the same vessel or the opposite cerebral artery.

Document Number: CDM10000146

Rev: AD

Appendix D. Informed Consent Form Template [attached]

Document Number: CDM10000146

Rev: AD

Appendix E. Sample Instructions for Use (IFU) [attached]

Document Number: CDM10000146

Rev: AD

Appendix F. Adaptive Design Plan [attached]

The primary endpoint is a comparison of the difference between the average weighted modified Rankin Scale score at 90 days post randomization between the two arms. Each mRS category is assigned a numerical value representing its clinical utility, based on the work by Rivero-Arias, et al and Hong and Saver, as described in the Adaptive Design Plan in Appendix F. of Protocol.	
The primary endpoint is the 90-day clinical outcomes assessed by the modified Rankin scale (mRS).
 
There will be two, hierarchically nested, co-primary analyses of this endpoint. The first primary endpoint analysis will consist of the difference between the average weighted modified Rankin Scale (mRS) score at 90 days post randomization between the active and control groups (weighted mRS analysis). For this analysis, each mRS category is assigned a numerical value representing its clinical utility, based on the work by Rivero-Arias, et al and Hong and Saver, as described in the Adaptive Design Plan in Appendix F. If this primary endpoint analysis is positive, the hierarchically nested second co-primary endpoint analysis will be conducted, and will be a comparison of the difference in proportion of functional independence (mRS 0-2) at 90 days post randomization between the active and control arm (dichotomous analysis).
	The nested co-primary endpoint was added for use when the study is considered in the regulatory setting. It will be used by FDA, which requested this additional criterion for regulatory consideration.
	Updated document style, headers, and footers to SNV standards	

STRYKER CONFIDENTIAL - THIS DOCUMENT CONTAINS CONFIDENTIAL AND PROPRIETARY INFORMATION THAT IS THE PROPERTY OF STRYKER CORPORATION. NEITHER THIS DOCUMENT NOR THE INFORMATION HEREIN MAY BE REPRODUCED, USED, OR DISCLOSED TO ANY THIRD PARTY WITHOUT THE PRIOR WRITTEN CONSENT OF STRYKER CORPORATION

1. OVERVIEW STATISTICAL PLAN

This document contains a detailed description of the Statistical Analysis Plan (SAP) for the data from the DWI or CTP Assessment with Clinical Mismatch in the Triage of Wake-Up and Late Presenting Strokes Undergoing Neurointervention (DAWN).

It provides specifications for the statistical analyses of the data to be prepared and presented for the purpose of demonstrating efficacy and safety to fulfill Food and Drug Administration (FDA) IDE requirements.

The structure and content of this SAP provides sufficient detail to meet the requirements identified by the FDA. This plan may be revised during the study to accommodate any study plan change request by FDA, to make changes to adapt to unexpected issues in study execution or data that affects planned analyses. The final plan will be issued prior to final data lock. Furthermore, as no analysis plan prepared in advance of the data can be definitive, the final report may contain additional tables, footnotes or statistical tests if warranted by the data obtained. The justification for any such additional analyses will be fully documented in the final report.

2. STUDY OBJECTIVES

2.1. Primary Objective

To evaluate the hypothesis that Trevo thrombectomy plus medical management leads to superior clinical outcomes at 90 days as compared to medical management alone in appropriately selected subjects experiencing an acute ischemic stroke when treatment is initiated within 6-24 hours after last seen well.

2.2. Secondary Objectives

To provide evidence that endovascular reperfusion with Trevo is associated with a significant reduction in median infarct size compared to the control group at 24 (-6/+24) hours post randomization.

STRYKER CONFIDENTIAL - THIS DOCUMENT CONTAINS CONFIDENTIAL AND PROPRIETARY INFORMATION THAT IS THE PROPERTY OF STRYKER CORPORATION. NEITHER THIS DOCUMENT NOR THE INFORMATION HEREIN MAY BE REPRODUCED, USED, OR DISCLOSED TO ANY THIRD PARTY WITHOUT THE PRIOR WRITTEN CONSENT OF STRYKER CORPORATION

3. STUDY DESIGN

The DAWN protocol is a prospective, randomized, multi-center, Phase II/III (feasibility/pivotal), adaptive, controlled trial, designed to demonstrate that mechanical thrombectomy using the Trevo Retriever with medical management is superior to medical management alone in improving clinical outcomes at 90 days in appropriately selected wake-up and late presenting acute ischemic stroke subjects.

Up to a total of 50 worldwide sites with ≤ 20 sites outside of the U.S will participate in the study. A maximum of 500 subjects are planned to be enrolled; 250 in the Treatment arm and 250 in the Control arm over an approximate 36-month recruitment period. Total study duration will be approximately 39 months (+/- 9 months), including one 24 (-6/+24) hours' MRI/MRA or CT/CTA and NIHSS assessment followed by Day 5-7, 30 (± 14), and Day 90 (± 14) clinical assessments.

3.1. Study Endpoints

3.1.1. Primary Endpoint

The primary endpoint is the 90-day clinical outcomes assessed by the modified Rankin scale (mRS).

There will be two, hierarchically nested, co-primary analyses of the primary outcome.

1. The first primary analysis will be a test of superiority for the active versus the control using a weighted utility value for each mRS score at 90-days. each mRS category is assigned a numerical value representing its clinical utility, based on the work by Rivero-Arias, et al and Hong and Saver, as described in the Adaptive Design Plan in **Appendix F**. [48-49]
2. If the first primary endpoint analysis is positive, the hierarchically nested second co-primary endpoint analysis will be conducted, and will be a test of superiority for the active versus the control comparing the proportion of functional independence (mRS 0-2) at 90 days post randomization.

Findings with this approach will be interpreted in the following manner:

STRYKER CONFIDENTIAL - THIS DOCUMENT CONTAINS CONFIDENTIAL AND PROPRIETARY INFORMATION THAT IS THE PROPERTY OF STRYKER CORPORATION. NEITHER THIS DOCUMENT NOR THE INFORMATION HEREIN MAY BE REPRODUCED, USED, OR DISCLOSED TO ANY THIRD PARTY WITHOUT THE PRIOR WRITTEN CONSENT OF STRYKER CORPORATION

- 1) The utility-weighted mRS analysis is neutral - the study will be considered to have a neutral result.
- 2) The utility-weighted mRS analysis is positive, and the nested dichotomous analysis is neutral - the study will be considered to have demonstrated benefit in reducing (shifting) disability but not benefit in increasing functional independence.
- 3) The utility-weighted mRS analysis is positive, and the nested dichotomous analysis is neutral. If the dichotomous mRS is also positive - the study will be considered to have demonstrated benefit in reducing (shifting) disability and also benefit in increasing functional independence.

